6.1 Sample Size Considerations

The criteria used to determine the sample size mimic common criteria to conclude bioequivalence, although they are not meant to fulfill regulatory guidance on showing bioequivalence in a strict sense.

In part 1, 16 participants will be randomized for treatment in order to obtain at least 12 evaluable participants. This sample size has been chosen to ensure that the ratios of the treatment geometric means can be estimated with sufficient precision.

In part 2, a maximum of 8 participants is considered adequate to assess the taste masking of RO7017773. This is based on previous experience not statistical analysis.

6.2 Randomization

Computer-generated randomization schemes will be produced by a PRA statistician prior to the start of the study for part 1 and part 2.

Subjects in part 1 who meet the eligibility criteria will be randomized to one of four treatment sequences from a 4-period Williams Latin Square as defined in [Table 1](#) prior to first dosing.

Table 1

Treatment Sequence	Period 1	Period 2	Period 3	Period 4
ABCD	A	B	C	D
BDAC	B	D	A	C
CADB	C	A	D	B
DCBA	D	C	B	A

Subjects in part 2 who meet the eligibility criteria will be randomized to one of the two treatment sequences as defined in [Table 2](#) prior to first dosing.

Table 2

Treatment Sequence	Period 1	Period 2
AB	A	B
BA	B	A

7.0 Overview of Planned Analysis

7.1 Changes from Protocol

There are no changes from the protocol.

7.2 Interim Analysis and Key Results

There will be no interim analyses or summaries of data provided prior to the delivery of the full set of post-lock tables, figures and listings (TFLs).

7.3 Final Analysis

Draft TFLs containing Safety, bioavailability, and food effect assessments will be provided after database lock. The sponsor will provide the PK concentration and parameter TFLs. After Sponsor comments have been incorporated, the TFLs will be finalized and incorporated in the first draft of the CSR.

8.0 Data Review

8.1 Data Management

Data handling and transfer will take place under the PRA Data Management Plan for the study.

8.2 Acceptance of Data for Summarization

Programming of analysis datasets and TFLs may be ongoing during the data management of the study. However, programming of analysis datasets and TFLs will be completed and quality controlled (QC'd) after database lock. Only quality assured (QA'd) results released by the Safety Laboratory, Bioanalytical Laboratory, or other external data source will be used for the programming of analysis datasets and TFLs for the final report. Any data values requiring investigation or corrections that are identified while

programming the analysis datasets and TFLs will be sent to the project Data Manager. If the issue affects the TFLs the Programmer or Statistician who identified the issue will follow it to resolution.

9.0 Definitions and General Analysis Methods

9.1 Analysis Data Presentation

9.1.1 Rounding

In listings data will be presented with the same precision as the original data. Derived data will be rounded for presentation purposes.

For all summaries, the mean and median will be presented to one decimal place greater than the data, standard deviation to two greater than the data, and the minimum and maximum will be presented to the same number of decimal places as the data. Percentages will be presented with one decimal.

The above rule can be applied directly to collected data. For derived data rounding will occur prior to summarization so a specific number of decimal places will have to be assumed to apply the above rounding rules for summary statistics.

Additional derived data will be rounded in the derived dataset as determined by the statistician.

9.1.2 Imputation

Unless otherwise noted, data will not be imputed.

9.1.3 Daylight Savings Time Adjustments

This study is not expected to fall over Daylight Savings Time and no adjustments for time change are planned.

9.1.4 Descriptive Statistics

Unless otherwise indicated, continuous variables will be summarized with the following descriptive statistics: n (number of observations), (arithmetic) mean, standard deviation (SD), minimum (min) value, median, and maximum (max) value.

Categorical data will be summarized with frequencies and percentages. Percentages by categories will be based on the number of subjects exposed within a treatment.

For categorical data the categories will be presented in the tables exactly as they appear in the CRF / Database.

9.1.5 Pooling

Summary statistics will be calculated by treatment (and timepoint, if applicable).

9.1.6 Unscheduled Measurements

Unscheduled and early termination measurements will be included in the listings. With the exception of unscheduled measurements used for baseline, unscheduled measurements will be excluded from the descriptive statistics and statistical analysis.

9.2 Analysis Data Definitions

9.2.1 Baseline Definition

Unless otherwise stated, baseline for post-dose evaluations is defined as the last observation recorded before the first study drug administration. The last observation can be an unscheduled / repeated measurement.

9.2.2 Treatment/Subject Grouping

Label	Grouping
Study Drug	Phase I RO7017773 capsule, Phase II RO7017773 tablet
Treatment	
In Part 1:
 
 A: Phase I capsule swallowed whole under fasted conditions B: Phase II tablet swallowed whole under fasted conditions C: Phase II tablet swallowed whole under fed conditions D: Phase II tablet dispersed in water under fasted conditions 
In Part 2:
 
 A: Phase II tablet containing flavor and/or sweetener dispersed in water under fasted conditions B: Phase II tablet without flavor and/or sweetener dispersed in apple juice under fasted conditions
Dose Level	█ mg of RO7017773

9.2.3 Common Variable Derivations

Variable	Data Type	Definition/Calculation
Analysis Study Day (Prior to First Dose)	All	Date of Measurement minus First Dose Date
Analysis Study Day (Post First Dose)	All	Date of Measurement minus First Dose Date +1

9.2.4 QC

The analysis datasets and the TFLs will be QC'd according to the general PRA EDS QC plan.

9.2.4.1 Critical Data

The QC plan requires datasets be classified as critical or non-critical. As the key objectives of this study are to characterize the pharmacokinetics and assess safety and tolerability the datasets considered critical are subject level, pharmacokinetic, and adverse events (ADSL, ADPC, ADPP, and ADAE).

9.2.5 AdaM Datasets and Metadata

The analysis datasets will be generated in accordance with Clinical Data Interchange Standard Consortium (CDISC) Analysis Data Model (AdaM) Version 2.1.

AdaM compliant datasets will be delivered to the sponsor. A define.xml file version 2 with the corresponding metadata will be included. Analysis results metadata are excluded.

9.3 Software

The statistical analysis and reporting will be done using SAS® for Windows™ Version 9.4 or higher (SAS Institute, Inc.).

9.4 Statistical Methods

9.4.1 Statistical Outlier Determination

No statistical outlier analysis is planned.

9.4.2 Predetermined Covariates and Prognostic Factors

There are no predetermined covariates or prognostic factors.

9.4.3 Hypothesis Testing

No formal hypothesis testing will be done.

9.5 TFL Layout

Table shells for safety and statistical analyses of PK parameters are provided with and approved as part of this SAP. Small changes to shell layout due to the nature of the data may be required after lock at the discretion of the PRA project statistician. Other changes to the shells may be out of scope. The TFLs will be provided as a single document in Adobe PDF format (in Letter format), and as individual files for each table, figure or listing in Rich Text Format (.rtf). Additional TFLs for PK concentrations and parameters will be provided by Roche.

10.0 Analysis Sets

Analyses	Safety Set	Pharmacokinetic Set
Disposition Summaries	✓	
Baseline Characteristics	✓	✓
Safety Assessments	✓	
PK Concentrations	✓	
PK Parameters		✓
Primary Analysis		✓

10.1 Safety Set

All subjects randomized to study treatment and who received at least one dose of the study drug, whether prematurely withdrawn from the study or not, will be included in the safety analysis. This set will be analyzed as treated.

10.2 Pharmacokinetic Set

All subjects who have received at least one dose of study drug and who have data from at least one post-dose sample will be included in the PK analysis population. Subjects will be excluded from the PK set if they significantly violate the inclusion or exclusion criteria, deviate significantly from the protocol, or if data are unavailable or incomplete which may influence the PK analysis. This set will be analyzed as treated.

11.0 Subject Disposition

The number and percentage of subjects randomized, dosed, and members of each analysis set will be presented. The number and percentage of subjects who withdrew from the study prematurely and a breakdown of the corresponding reasons for withdrawal will also be presented.

12.0 Protocol Deviations

Protocol deviations will be included in the CSR.

13.0 Demographic and Baseline Characteristics

13.1 Demographics

Subject demographics will be summarized overall. The summary will include the subjects' age (years), sex, race, ethnicity, weight (kg), height (cm), BMI (kg/m²), female reproductive status, and method of contraception. Demographics will be summarized for the Safety Set and PK Set.

All demographic data as collected during the screenings visit will be listed by subject.

13.2 Medical History

Medical history will be listed by subject.

13.3 Other Baseline Characteristics

Urine drug and alcohol screen, and non-compliance with inclusion/exclusion criteria (if any) will be listed by subject.

14.0 Concomitant Medications

Concomitant medication will be listed by subject. Medications with an end date prior to the first dose of study drug will be considered prior medications and will be noted in the listing. If a partial date allows a medication to be considered concomitant it will be categorized as such.

15.0 Treatment Compliance and Exposure

The number of subjects receiving each dose of study drug will be summarized.

Exposure data will be listed by subject.

16.0 Pharmacokinetic Analyses

16.1 Pharmacokinetic Variables

The reporting of pharmacokinetic concentrations and calculation of pharmacokinetic parameters will be in accordance with Roche clinical pharmacology guiding principles for calculation and analyses of non-compartmental pharmacokinetic parameters version 4.

Individual plasma concentrations of RO7017773 and metabolites (if appropriate) will be presented together with descriptive statistics by treatment.

Individual plasma PK parameters of RO7017773 and metabolites (if appropriate) will be estimated using non-compartmental methods with WinNonlin® for each subject by treatment.

Individual values of calculated PK parameters will be presented together with their descriptive statistics by treatment. The following descriptive statistics will be used: number of subjects, mean, geometric mean, SD, CV, geoCV, median, min, and max. For t_{max}, only median, min and max will be presented.

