##### **9.4.3.1 Pharmacokinetic Parameters**

The primary RO7017773 PK study variable will be the AUC (AUC0-inf if it can be derived, otherwise truncated as appropriate) and Cmax. For Treatment C of Part 1, Tmax is additionally considered as primary PK variable. All other PK parameters will be regarded as secondary.

The following PK parameters of RO7017773 will be read from the concentration versus time profiles or estimated using non-compartmental methods where appropriate:

- Tmax : Time to maximum plasma concentration
- Cmax : maximum observed plasma concentration
- AUC0-t : area under the plasma concentration-time curve up to time t
- AUC0-last : area under the plasma concentration-time curve up to the last measurable concentration

- $AUC_{0-\infty}$ : area under the plasma concentration-time curve extrapolated to infinity
- $T_{1/2}$  : apparent terminal half-life, computed as  $\ln(2)/\lambda_z$
- $CL/F$ : apparent oral clearance, calculated as Dose/ $AUC_{0-\infty}$

Additional PK parameters may be reported as appropriate.

All pharmacokinetic concentration and calculated PK parameters for RO7017773 will be presented in individual listings and summary tables (including descriptive summary statistics: mean, standard deviation, coefficient of variation, median, minimum, and maximum), and graphs (including concentration vs. time plots on linear and semi-logarithmic scales) as appropriate.

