## 9.5 STATISTICAL ANALYSIS

### Part 1:

The following linear statistical model will be applied to the log-transformed, dose normalized PK variables AUC ( $AUC_{0-\infty}$  if it can be derived, otherwise truncated as appropriate) and  $C_{max}$  from Part 1:

$$Y_{ijkm} = \mu + \tau_i + \pi_k + \omega_j + s_m + \varepsilon_{ijkm}.$$

In this model  $\mu$  denotes the general mean of the log transformed variables,  $s_m$  is the random effect for participant m,  $\tau_i$  are fixed effects for treatment i ( $i = 1, \dots, 4$ ),  $\pi_k$  are fixed effects for period k ( $k = 1, \dots, 4$ ), and  $\omega_j$  are fixed effects for sequence j ( $j = 1, \dots, 4$ ). The random participant effects and the random errors  $\varepsilon_{ijkm}$  are assumed to be independent and normally distributed with zero means and standard deviations  $\sigma_s$  and  $\sigma_\varepsilon$ , respectively.

From the model, 90% two-sided confidence intervals for the geometric mean ratios will be derived comparing treatments A vs B (assessing the primary objective of Part 1), as well as treatments B vs D and B vs C (assessing the first two secondary objectives).

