5.2 Secondary

- To assess the PK of RO7017773 Phase II tablet formulation dispersed in water or swallowed whole.
- To assess the effect of a high-fat meal on the PK (PK) of a single oral dose of RO7017773 Phase II tablet formulation.
- To assess the taste of RO7017773 Phase II tablet formulation without sweetener and flavor dispersed in water.
- To assess the PK of RO7017773 Phase II tablet formulation containing sweetener and flavor dispersed in water and the RO7017773 Phase II tablet formulation without sweetener and flavor dispersed in apple juice.
- To evaluate the safety and tolerability of single oral doses of different RO7017773 formulations in healthy participants.

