16.1.1.1 Part 1 Bioavailability and Food Effect

The bioavailability of RO7017773 administered as a Phase I capsule compared to a Phase II tablet, the bioavailability of RO7017773 administered as a Phase II tablet dispersed in water compared to a Phase II tablet swallowed whole, and the effect of a high-fat, high calorie meal on the bioavailability of RO7017773 administered as Phase II tablet, will be assessed.

90% confidence intervals (CIs) of the geometric least-squares (LS) mean ratios of the RO7017773 plasma PK parameters Cmax and AUCinf will be calculated. If AUCinf cannot be derived, Cmax and AUClast will be used. The following linear mixed effects model will be implemented using the natural log-transformed parameters, where τ_i are fixed effects for treatment ($i=1, \dots, 4$), π_k are fixed effects for period ($k=1, \dots, 4$), ω_j are fixed effects for sequence ($j=1, \dots, 4$), and s_m is the random effect for subject m . The random subject effects and the random errors ϵ_{ijkm} are assumed to be independent and normally distributed with zero means and standard deviations σ_s and σ_ϵ , respectively.

$$Y_{ijkm} = \mu + \tau_i + \pi_k + \omega_j + s_m + \epsilon_{ijkm}$$

Estimates on the original scale of measurement will be obtained by exponentiating point estimates on the natural log scale. Geometric LS means will be provided for each treatment. In all comparisons, treatment B will be used as the reference. No adjustments will be made for multiplicity.

The following SAS PROC MIXED pseudo-code may be used:

```
proc mixed data = adpp;
  by analyte parameter;
  class treatment period sequence subject;
  model ln(aval) = treatment period sequence/ddfm=kr;
  random subject;
  lsmeans treatment / alpha = 0.1;
  estimate "A vs B (capsule vs tablet)" treatment 1 -1 0 0 /e cl alpha=0.1;
  estimate "C vs B (fed vs fasted)" treatment 0 -1 1 0 /e cl alpha=0.1;
  estimate "D vs B (dispersed in water vs swallowed)" treatment 0 -1 0 1 /e
  cl alpha=0.1;
```

run;

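### Tmax is a primary PK variable for the fed treatment, but no fed-versus-fasted Tmax estimate or interval is planned

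*SAP*

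**What the plan says.** Protocol 9.4.3.1 takes AUC and Cmax as the primary PK variables and says that, for Treatment C of Part 1, Tmax "is additionally considered as primary PK variable". All remaining parameters are secondary. Treatment C is the tablet swallowed under fed conditions; Treatment B is the same tablet fasted.

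Protocol 9.5 applies the Part 1 crossover model to log-transformed AUC and Cmax and derives 90% intervals for A vs B, B vs D and B vs C. SAP 16.1.1.1 does the same: intervals for ratios of the "RO7017773 plasma PK parameters Cmax and AUCinf will be calculated", with AUClast as the fallback for AUC. Its fed-versus-fasted contrast is an estimate statement inside that model. It also fixes the direction: "In all comparisons, treatment B will be used as the reference".

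SAP 16.1 presents individual parameter values with descriptive statistics by treatment, and for Tmax "only median, min and max will be presented". In SAP Appendix 3, Table 14.2.1 is the only Part 1 PK comparison table.

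The food effect is a secondary objective (SAP 5.2: "To assess the effect of a high-fat meal on the PK"), and SAP 9.4.3 states "No formal hypothesis testing will be done".

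**The concern.** Tmax has primary status for one treatment only, the fed one, so it was evidently singled out for the food-effect question. Yet it is the one primary PK variable without a planned fed-versus-fasted estimate.

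Two by-treatment medians with their ranges say nothing about how much the shift varies between participants or how well it is estimated. The crossover was chosen so that each participant serves as his or her own control (Protocol 4.2), and a by-treatment summary drops that pairing. Anyone wanting an interval would have to derive it from the individual values, with a method chosen after the data are known.

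**Working it through.** **1. The passages side by side (Part 1, fed versus fasted)**

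| Variable | Status for Treatment C (Protocol 9.4.3.1) | C vs B estimate with 90% CI (Protocol 9.5, SAP 16.1.1.1) | Other reporting (SAP 16.1) |
|---|---|---|---|
| AUC | primary | yes | individual values, full descriptive statistics |
| Cmax | primary | yes | individual values, full descriptive statistics |
| Tmax | primary | no | individual values; median, min, max by treatment |

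The gap is in both documents. The SAP does not depart from Protocol 9.5 here. There is no plan figure to reproduce on this point.

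**2. Is a paired interval feasible at the planned size?**

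SAP 6.1 plans 16 randomized and at least 12 evaluable. For n pairs there are M = n(n+1)/2 Walsh averages (d_i + d_j)/2 with i ≤ j. The Hodges-Lehmann estimate is their median. With T the signed-rank statistic under its exact null distribution, take the largest k with P(T ≤ k) ≤ 0.05. The interval runs from the (k+1)th smallest to the (k+1)th largest Walsh average, with coverage 1 − 2P(T ≤ k).

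- n = 12: M = 78, k = 17, P = 189/4096 = 0.0461. Interval: 18th to 61st. Coverage 1 − 2(0.0461) = 90.8%.
- n = 16: M = 136, k = 35, P = 3062/65536 = 0.0467. Interval: 36th to 101st. Coverage 1 − 2(0.0467) = 90.7%.

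Both figures assume untied, symmetric differences.

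**3. What the by-treatment summary hides**

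Assumed values in hours, 12 participants:

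- B: 0.5, 1, 1, 1, 1.5, 1.5, 2, 2, 2, 3, 3, 4 (median 1.75, range 0.5 to 4)
- C: 1, 1.5, 2, 2, 2, 3, 3, 3, 4, 4, 6, 6 (median 3.0, range 1 to 6)

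The planned summary is identical however these values are paired. The difference of medians is 3.0 − 1.75 = 1.25 h. The paired results are:

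| Pairing of the same values | Typical 90% CI, C minus B | Lower bound above 0 |
|---|---|---|
| Same order (correlation 0.94), estimate 1.125 h | 0.75 to 1.50 h | yes |
| Random pairings, correlation 0.3 to 0.6, typical estimate 1.25 h | 0.5 to 2.0 h | about 99% of pairings |
| Random pairings, correlation −0.05 to 0.05 | 0.25 to 2.25 h | 57% to 58% of pairings |

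The second interval is twice as wide as the first (2.0 − 0.5 = 1.5 h against 1.50 − 0.75 = 0.75 h). The difference of medians lies close to the paired estimates throughout, so what the summary lacks is precision, not the rough size of the shift.

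**4. Effect of tied sampling times**

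The sampling times are redacted. Coverage was simulated with 10,000 runs per setting. Assumptions: fasted Tmax lognormal with median 2 h and CV 50%; log-scale within-subject correlation 0.3 or 0.6; shift 0, 1 or 2 h; n = 12 or 16.

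| Assumed sampling grid | Coverage of the nominal 90% interval |
|---|---|
| untied | 90.4% to 91.2% |
| 15 times | 95.5% to 97.4% |
| 10 times | 96.4% to 98.0% |
| 7 times | 97.7% to 99.6% |

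Median width was 0.75 to 1.5 h on the grids, against 0.81 to 1.28 h untied. Ties make the interval conservative, but it stays usable.

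**5. Period**

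From the sequence table in SAP 6.2, the period of C minus the period of B is +1 (ABCD), +3 (BDAC), −3 (CADB) and −1 (DCBA). These sum to 0, so with balanced sequences a linear period trend cancels in the mean difference. Unequal dropout would disturb this.

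**The case against.** The case for leaving the plan alone has four parts.

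- **A primary label does not promise an interval.** Protocol 9.4.3.1 ranks variables; Protocol 9.5 then says which are modelled, and the SAP follows it. The sample-size text in SAP 6.1 ties precision to ratios of geometric means. Tmax is read from discrete sampling times and does not fit that framework, so describing it is a coherent choice in a study without tests. This stands in part: no rule is broken. But the absence of testing cannot be the reason, because AUC and Cmax get intervals for the same secondary objective under the same rule. A paired difference with an interval needs no log-scale model and is still descriptive.
- **The individual values are presented.** True: the information is not lost. What is missing is a prespecified summary of it. SAP 3.0 would let an added analysis be identified in the study report without a SAP update, but the method would then be chosen with the data in hand.
- **The contrast may exist elsewhere.** SAP 16.1 cites sponsor "guiding principles for calculation and analyses of non-compartmental pharmacokinetic parameters version 4", the sponsor supplies the PK parameter outputs (SAP 7.3 and 9.5), and the table shells are a separate document. None of these was available. This stands and limits confidence. Against it, SAP 7.3 counts the food-effect assessment separately from the sponsor's PK outputs, and no text mentions a Tmax contrast in any of these sources.
- **Little depends on it.** At moderate correlation the lower bound is above zero in about 99% of the illustrative pairings, and no visible decision rule uses Tmax precision. This also stands, and it keeps the point modest.

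**Conclusion.** The concern holds. A variable that the protocol makes primary for the fed treatment has no planned fed-versus-fasted estimate or interval in the available text, while the other two primary variables have both. The consequence is missing precision: in the illustration, one and the same planned table fits intervals from 0.75 to 1.50 h up to about 0.25 to 2.25 h. Those figures rest on assumed Tmax values and pairings, and the tied-data coverage rests on assumed sampling grids. The absence of the contrast is read from the protocol and SAP alone, so confidence is medium. The change should be made because it is cheap. The Part 1 primary comparison of capsule with tablet is not affected.

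**What to change.** In SAP 16.1.1.1 and Table 14.2.1, add for Tmax the within-subject difference C minus B in participants with Tmax in both periods. Report the number of pairs, the Hodges-Lehmann median difference and the signed-rank 90% interval. Label it descriptive, and state that it is conservative with tied sampling times and not adjusted for period. C minus B keeps Treatment B as the reference. Record the addition in SAP 7.1, which now declares no changes from the protocol.

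Cost: a short paragraph, one table row with its shell, and one entry in SAP 7.1. It needs no new data, no larger sample and no change to the AUC and Cmax model. The drawback is that actual coverage may run from about 95% to almost 100% rather than 90%.

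If the sponsor's PK outputs already contain this contrast, a cross-reference in SAP 16.1.1.1 is enough. A single line declaring Tmax descriptive only would reconcile the plan with Protocol 9.4.3.1, but would still give no precision.
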